8.7.1. Prohibited Medications and Procedures

Treatment with the following concomitant medications is prohibited during the study:

- Treatment with a live (attenuated) vaccine; below is a list of examples of such vaccines. Refer to study manual for a current, comprehensive list of prohibited vaccines

Chickenpox (Varicella)	Oral typhoid
FluMist-Influenza	Rubella
Intranasal influenza	Smallpox (Vaccinia)
Measles (Rubeola)	Yellow fever
Measles-mumps-rubella combination	Bacillus Calmette-Guerin
Measles-mumps-rubella-varicella combination	Rotavirus
Mumps	Varicella Zoster (shingles)
Oral polio (Sabin)	

- Treatment with an investigational drug (other than dupilumab)
- Treatment with immunomodulating biologic agents, including anti-IgE
- Treatment with allergen immunotherapy
- Treatment with systemic (oral, IV, IM, SC) corticosteroids for a duration of more than 5 continuous days, more than 15 days in total, or within 2 days prior to DBPCFCs
- Treatment with any agents known or likely to interact with epinephrine (eg, beta blockers, ACE-inhibitors, tri-cyclic antidepressants, or other drugs)
- Treatment with antihistamines within 5 days prior to screening and within 5 days prior to SPTs and day 1 of DBPCFCs

The following concomitant procedures are prohibited during study participation:

- Major elective surgical procedures

8.7.2. Permitted Medications

Other than the prohibited medications listed in Section 8.7.1, treatment with concomitant medications is permitted during the study.

Medications used to treat chronic disease other than those listed in Section 8.7.1 are also permitted. Patients/parents/caregivers should be advised not to reduce or stop taking medications for concomitant conditions throughout the entire study period. If there is any question regarding whether a concomitant medication may be used during the study, the study site should contact the medical monitor.

9. STUDY SCHEDULE OF EVENTS AND PROCEDURES

9.1. Schedule of Events

Study assessments and procedures are presented by study period and visit in [Table 1](#).

Table 1: Schedule of Events

Study Procedure	Screening		Treatment Period														Follow-up		UV	ET
	V1	V1a	Baseline V2	V3 phone	V4 clinic	V5 phone	V6 clinic	V7 phone	V8 clinic	V9 phone	V10 clinic	V11 phone	V12 clinic	V13 phone	EOI V14 clinic	V15	EOS V16	if applicable		
Day	-57 to -43	-42 to -15	1	15	29	43	57	71	85	99	113	127	141	155	169	211	253			
Week				2	4	6	8	10	12	14	16	18	20	22	24	30	36			
Visit Window (days)				±3	±3	±3	±3	±3	±3	±3	±3	±3	±3	±3	±3	±3	±3			
Screening/Baseline:																				
Inclusion/Exclusion	X		X																	
Informed Consent/Assent	X																			
Medical History	X																			
Demographics	X																			
Enrollment			X																	
Epi injection training			X																	
Training on Study Drug Administration			X																	
Treatment:																				
Administer Study Drug ¹			X	X	X	X	X	X	X	X	X	X	X	X						
Study Drug Dispensation/Account			X		X		X		X		X		X		X					
Phone call to collect AEs, Conmeds and IP compliance				X		X		X		X		X		X						
Concomitant Meds and Tx	X	X	X		X		X		X		X		X		X	X	X	X	X	
Efficacy²:																				
DBPCFC ^{2, 3,4}		X													X		X ¹⁰			
Peanut SPT ³	X																			
Titrated Peanut SPT ^{3,7}			X		X				X						X		X		X	
FAQLQ			X						X						X		X			
Safety:																				
Weight ⁵	X		X		X		X		X		X		X		X	X	X	X	X	

Study Procedure	Screening		Treatment Period													Follow-up		UV	ET
	V1	V1a	V2 Baseline	V3 phone	V4 clinic	V5 phone	V6 clinic	V7 phone	V8 clinic	V9 phone	V10 clinic	V11 phone	V12 clinic	V13 phone	EOT V14 clinic	V15	EOS V16	if applicable	
Day	-57 to -43	-42 to -15	1	15	29	43	57	71	85	99	113	127	141	155	169	211	253		
Week				2	4	6	8	10	12	14	16	18	20	22	24	30	36		
Visit Window (days)				±3	±3	±3	±3	±3	±3	±3	±3	±3	±3	±3	±3	±3	±3		
Height ⁵	X																		
Vital Signs ⁵	X	X	X		X		X		X		X		X		X	X	X	X	X
Physical Examination ⁵	X	X							X						X		X		X
Spirometry ⁶	X	X							X						X		X		X
Adverse Events ⁵	X	X	X		X		X		X		X		X		X	X	X	X	X
Laboratory Testing:																			
HIV Ab, HBsAg, HBcAb, Hep C Ab ⁵	X																		
Hematology/Chemistry ⁵	X		X						X						X		X	X	X
FeNO Test ⁶		X							X						X		X		X
Pregnancy Test (WOCBP) ⁵	S	U	U		U		U		U		U		U		U	U	S		U
Urinalysis ⁵	X	X	X						X						X		X	X	X
Total IgE ⁵			X						X						X		X		X
Peanut sIgE, sIgG, and sIgG4 ⁵	X		X		X		X		X		X				X	X	X		X
Research Samples (serum/plasma) ⁵		X	X						X						X		X		X
Blood samples for additional exploratory ⁵ research ⁷			X						X						X		X		X
PK/Drug Concentration and ADA Samples⁸:																			
PK/Drug conc. sample			X				X		X						X		X		X
ADA sample			X						X						X		X		X
Genomic DNA sample⁹:																			

Study Procedure	Screening		Treatment Period													Follow-up		UV	ET
	V1	V1a	V2 Baseline	V3 phone	V4 clinic	V5 phone	V6 clinic	V7 phone	V8 clinic	V9 phone	V10 clinic	V11 phone	V12 clinic	V13 phone	EOT V14 clinic	V15	EOS V16	if applicable	
Visit																			
Day	-57 to -43	-42 to -15	1	15	29	43	57	71	85	99	113	127	141	155	169	211	253		
Week				2	4	6	8	10	12	14	16	18	20	22	24	30	36		
Visit Window (days)				±3	±3	±3	±3	±3	±3	±3	±3	±3	±3	±3	±3	±3	±3		
Buccal swab samples for DNA			X																

WOCBP = women of childbearing potential

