6.1. Study Description and Duration

This is a phase 2, multicenter, single-arm open-label POC study in pediatric patients aged 6 to 17 years inclusive who are allergic to peanut, to evaluate the effects of dupilumab on tolerability of peanut protein during a DBPCFC. The study consists of an 8-week screening period, 24-week open-label treatment period with dupilumab, followed by a 12-week safety follow-up period (Figure 1).

Figure 1: Schematic of Study Design

Screening

After obtaining informed consent/assent, patients will be assessed for eligibility during a 2-part screening period. During screening visit 1 (day -57 to day -43), patients will undergo a medical history, physical examination, spirometry, peanut SPT, and laboratory testing (including sIgE) and will be evaluated for the study eligibility criteria.

During screening visit 1a (day -42 to day -15), under direct study investigator monitoring, patients will undergo a DBPCFC to confirm current peanut allergy. This will consist of 5 doses of peanut protein with a dose given every 15 to 30 minutes in increasing amounts up to a cumulative total of 144 mg of peanut protein (Appendix 1). Vital signs will be assessed every 15 to 30 minutes. If the

study team suspects a reaction may be developing, they may exercise their clinical judgment to separate doses by up to an additional 30 minutes (1 hour maximum between doses). The matching placebo challenge will consist of placebo material (oat protein) given also in 5 doses. Both peanut and oat protein will be concealed in a food that masks the taste. The food challenges will be performed on different days (1 day placebo [oat] protein, 1 day peanut protein, with order determined at random) at least 24 hours, but not more than 7 days, apart. The doses will be 1, 3, 10, 30, and 100 mg of peanut protein (or placebo). Both food challenge days (placebo and peanut) must be done to evaluate eligibility.

Before each challenge, the patient will have a physical assessment by a trained physician's assistant, registered nurse, nurse practitioner, and/or physician of the study team who is blinded to the testing material. The supervising investigator will also be blinded to testing material.

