Reactions will be scored using the Consortium of Food Allergy Research (CoFAR) grading system (see [Appendix 2](#)). The DBPCFC will be stopped when the blinded assessor finds symptoms and/or signs that indicate a definite objective allergic reaction (CoFAR grading system [see [Appendix 2](#)]) has occurred based on clinically significant changes in reported symptoms, physical findings, or vital signs that the patient is experiencing to the challenge material. The patient will be observed for a minimum of 2 hours after the final administered dose and discharged only when deemed clinically stable by a study physician. All food challenges will be performed under physician supervision. If the patient does not experience dose-limiting symptoms at or before the 100 mg challenge dose (≤ 144 mg cumulative) of peanut protein or if he/she experiences symptoms at any dose of placebo, he/she will not be enrolled in the study. Investigator/site personnel will be unblinded only to the results of the screening food challenge upon completion of the second part of the challenge to assess eligibility. A 2-week washout period is needed after the screening DBPCFC where peanut was given. All other on-study food challenges in the study will remain blinded to the clinic study team.

Treatment Period

Patients with a history of confirmed peanut allergy signs and symptoms at screening who continue to meet eligibility criteria at baseline will be enrolled.

Dupilumab will be dosed SC on day 1 at least 14 days after the screening DBPCFC (this interval was selected to ensure that accurate biomarker values at baseline are captured) and the dose will not be changes regardless of weight gain or loss:

- patients weighing ≥ 20 kg and < 60 kg will receive dupilumab 200 mg Q2W following a loading dose of 400 mg on day 1
- patients weighing ≥ 60 kg will receive dupilumab 300 mg Q2W following a loading dose of 600 mg on day 1

Study drug may be administered in the clinic on day 1 by the study team, patient's caregiver, or patient. Patient and/or caregiver will be trained on how to store, handle, prepare, and administer study drug at home Q2W. The last dose of study drug will be at week 22. For patients under 12 years of age, adult caregiver will need to administer the study drug injections.

Patients will have monthly clinic visits and phone calls in-between visits to collect AEs, concomitant medications and compliance to study drug administration.

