6.1.2. Study Design Safety Considerations**The design considers important safety issues:**

- All DBPCFC visits will be supervised in-clinic setting where trained study physicians are available
- Standing orders from a medical doctor are provided for all clinical study personnel to initiate treatment of reactions immediately (ie, prior to medical doctor notification), including IM administration of epinephrine, based on their own clinical judgment
- A crash cart with pediatric equipment will be available in close proximity (within 50 feet) of all patient clinic rooms
- A code team is available
- Dosing allergic symptoms and AEs will be captured throughout the study
- Patients will be prescribed an epinephrine auto-injector (if not prescribed by a treating clinician previous to study entry) and all patients/Caregivers will be trained in its use. Patients will be advised to carry the autoinjector with them at all times.
- Patients /caregivers will be cautioned against patients consuming any peanuts or peanut-containing foods other than the peanut allergen challenge while on study
- The dupilumab clinical development program in food allergy independent data monitoring committee (IDMC) will provide oversight of patient safety. The IDMC will provide Regeneron and Sanofi with appropriate recommendations on the conduct of the food allergy clinical studies to ensure the protection and safety of the patients enrolled in these studies.

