7.2.1. Inclusion Criteria

A patient must meet the following criteria to be eligible for inclusion in the study:

1. Age 6 to 17 years (inclusive).
2. Patient has a clinical history of allergy to peanuts or peanut-containing foods (symptom[s] of reaction due to exposure).
3. Experience dose-limiting symptoms at or before the 100 mg challenge dose (≤ 144 mg cumulative) of peanut protein (measured as 200 mg of peanut flour) on screening DBPCFC conducted in accordance with PRACTALL (Practical Issues in Allergology, Joint United States/European Union Initiative) guidelines. And not experiencing dose limiting symptoms to placebo
4. Serum IgE to peanut of ≥ 10 kUA/L and/or a SPT to peanut ≥ 8 mm compared to a negative control.

5. Patients/legal guardians must be trained on the proper use of the epinephrine autoinjector device to be allowed to enroll in the study.
6. Patients with other known food allergies must agree to eliminate these other food items from their diet so as not to confound the safety and efficacy data from the study.
7. Written informed consent from parent/guardian.
8. Written assent from minor patients as appropriate (eg, above the age of 6 years or the applicable age per local regulatory requirements).
9. Willing and able to comply with all clinic visits and study-related procedures.

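### Epinephrine autoinjector training is scheduled only at V2 (day 1), after the V1a screening peanut challenge, and no other provision requires it earlier

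*Protocol*

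**What the plan says.** Table 1 in Protocol Section 9.1 has one row for this training, "Epi injection training", with one mark, at V2 on day 1. That is also the column marked for enrollment. V1 and V1a are blank, and the schedule in SAP 10.2 is the same.

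The screening food challenge is at V1a, day -42 to day -15. Section 6.1 adds: "Dupilumab will be dosed SC on day 1 at least 14 days after the screening DBPCFC".

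Two other provisions create the duty to train:

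- Section 7.2.1, criterion 5: "Patients/legal guardians must be trained on the proper use of the epinephrine autoinjector device to be allowed to enroll in the study".
- Section 6.1.2, on supply of the device: "Patients will be prescribed an epinephrine auto-injector (if not prescribed by a treating clinician previous to study entry". The same bullet says that all patients and caregivers will be trained and advised to carry the device. It names no visit.

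Eligibility is looked at twice. Table 1 marks "Inclusion/Exclusion" at V1 and V2, and Section 6.1 says that at screening visit 1 patients "will be evaluated for the study eligibility criteria".

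After the challenge, Section 6.1 requires at least 2 hours of observation, with the patient "discharged only when deemed clinically stable by a study physician". Footnote 4 in Section 9.1.1 repeats the 2 hours. Neither mentions a device or training.

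**The concern.** The challenge at V1a is meant to provoke a reaction, and only children who have dose-limiting symptoms to peanut at or before the 100 mg dose are enrolled. Every enrolled child will therefore have had a provoked reaction and gone home before the only visit at which training is scheduled.

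Children who fail screening at V1a never reach V2, so the schedule gives them no training. Some of them may have just reacted to peanut, because symptoms on the placebo day also exclude: "if he/she experiences symptoms at any dose of placebo, he/she will not be enrolled in the study".

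The two challenge days are 24 hours to 7 days apart, and under Appendix 1 the clinic staff stay blinded to the order until the second is complete. A child who goes home after the first day does so without the staff having been told which material was given.

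What is at stake is readiness at home after a planned exposure, in a study that already treats this training as a condition of entry.

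**Working it through.** This is a check of visit order. The protocol gives no figure of its own to reproduce.

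**1. Interval from V1a to scheduled training.** The study-day convention in SAP 5.3 has no day 0: before treatment, study day = event date - first-dose date; from treatment on, 1 is added. Day -k is therefore k calendar days before day 1.

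- Latest V1a, day -15: 15 days before V2.
- Earliest V1a, day -42: 42 days before V2.
- Floor in the Section 6.1 text: 14 days.

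Training at V2 cannot precede or accompany the peanut challenge under either rule.

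**2. Whether training at V1 would come first.** V1 is day -57 to -43.

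- Shortest V1 to V1a: day -43 to day -42, 43 - 42 = 1 day.
- Longest: day -57 to day -15, 57 - 15 = 42 days.

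V1 always precedes V1a, by as little as 1 day.

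**3. Whether another provision forces earlier training.**

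| Provision | What it requires | Deadline before V1a? |
|---|---|---|
| Table 1 | Training at V2 | No |
| 7.2.1, criterion 5 | Training in order to enroll; enrollment is marked at V2 | No; training on day 1 can satisfy it |
| 6.1.2 | Prescription if lacking; training for all | No visit named |
| 3.3.2 | Reminder to carry the autoinjector | No; presumes a device |
| 6.1 and 9.1.1, footnote 4 | 2 hours of observation; clinical stability (6.1) | No mention of device or training |

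Table 1 is the only place that assigns a visit, and it assigns V2.

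**4. Size.** The only related rate is in Section 3.3.2: under 0.1% for life-threatening anaphylactic reactions, with no unit stated. Assume that it applies per patient per peanut challenge. With N children challenged at V1a, the expected number is below 0.001 x N.

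- N = 24 (planned enrollment only): 24 x 0.001 = 0.024.
- N = 48 (an assumption that half of those challenged fail screening): 48 x 0.001 = 0.048.

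These bounds combine events in clinic and after discharge, and leave out milder reactions. The number challenged and the share of families without a device are not stated, so the group affected cannot be sized.

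**The case against.** The strongest reply is that the obligation exists and only its timing is unstated. Section 6.1.2 binds sites as much as Table 1 does. It covers all patients, and its test for a prescription looks back to study entry, so it can be read as starting there. Eligibility is evaluated at V1, and Section 6.1 enrolls those who continue to meet the criteria at baseline, which suggests that a criterion such as number 5 was raised earlier. On that reading the V2 mark records training at enrollment and is not the earliest permitted date.

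This is a fair reading, and nothing bars earlier training. But study entry is not defined, criterion 5 is tied to enrollment, and criterion 3 (the challenge reaction) cannot be met at V1, so continuing to meet the criteria cannot mean that all were met there. The reading permits early training without requiring it.

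Four further points stand and limit the weight:

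- Cover during challenges is strong: study physicians, standing epinephrine orders, a crash cart and a code team (Section 6.1.2).
- All patients have a clinical history of peanut allergy, and the protocol expects some to have a device already.
- The manual of procedures (Section 8.1.1) and study reference manual (Section 10.4.1) are not among the documents and might set an earlier time.
- Making possession of a device a condition of discharge would cost more than a mark in a table. The protocol promises a prescription, names no supply route, and allows V1 to precede V1a by a single day.

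A reader might infer that families are in fact being sent home untrained or without a device, or that the whole 15 to 42 days is risk created by the challenge. The documents support neither. They show a schedule that allows late training, not what sites do. Section 6.1.3.2 defines anaphylaxis as rapid in onset, and most of the interval carries the child's ordinary risk of accidental exposure.

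**Conclusion.** The point holds as a minor patient-safety improvement. The only scheduled training comes after the screening challenge, and a site can meet every stated requirement without training families before it. For those who fail screening at V1a the schedule provides no training at all.

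The conclusion rests on the protocol and SAP as written and would lapse if a study manual already sets training before V1a; Table 1 would then only need to be brought into line. No harm is demonstrated: there is no post-discharge reaction rate, and the rough bound of 0.024 events among 24 enrolled patients depends on an assumed unit and includes reactions treated in clinic. Sample size, endpoints and analyses are untouched.

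**What to change.** - In Protocol Table 1, mark epinephrine training at V1, or at V1a before the first challenge dose. Keep the V2 mark as a refresher.
- In Section 6.1.2, state that any patient without an autoinjector is prescribed one at V1, and that the site checks before the challenge that the family has it.
- Update the schedule in SAP 10.2 for consistency only.

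Decisions on when to give epinephrine stay with the clinicians. No visit is added. The cost is a few minutes of training for families who later fail screening and a short check before the challenge. For any family without a device, the prescription must also be filled before V1a. Where V1 and V1a would fall a day apart, the challenge may have to be booked later in its day -42 to -15 window.

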9.1.1. Footnotes for the Schedule of Events Table

1. Study drug will be administered in the clinic on day 1 by the study team, patient's caregiver, or patient. With adequate training, study drug may be administered at home Q2W for the remaining injections. Patient/caregiver will complete an injection log to document compliance with injection of study drug and to document any AEs and concomitant medications.
2. During DBPCFC, vital signs will be collected every 15 to 30 minutes. After initial DBPCFC dose, only pulse and blood pressure need to be taken as part of safety monitoring.
3. Patients should not take antihistamines within 5 days prior to SPTs and day 1 of the DBPCFCs.
4. The food challenges (DBPCFC) will be performed on different days (1 day placebo [oat] protein, 1 day peanut protein, with order determined at random) at least 24 hours, but no more than 7 days, apart and not within 24 hours of a dose of study drug. After the last dose of the DBPCFC, the patient will be monitored for at least 2 hours and then discharged from the clinic.
5. Assessments will be performed before the administration of study drug.
6. FeNO measurement and spirometry will be performed on the same day, except for visit 1, in which only spirometry is performed. If the DBPCFC is scheduled on the day of the visit, then both FeNO measurement and spirometry will be performed twice before the patient goes home: once before DBPCFC, once after DBPCFC. FeNO should be done prior to spirometry.
7. On the day of the DBPCFCs, blood draws for exploratory research, including TruCulture, basophil sensitivity, and peripheral blood mononuclear cells (PBMC) samples will be performed before the DBPCFC is performed. On the day of the DBPCFC, titrated SPTs will be performed before the DBPCFC.
8. Samples for PK and ADA analysis should be collected prior to drug administration.
9. Two buccal swabs for genomic analysis can be collected on day 1 or any day after day 1.
10. Only patients who passed a DBPCFC of at least 444 mg (cumulative) at week 24 will undergo a final DBPCFC (up to 2044 mg cumulative).

9.1.2. Early Termination Visit

Patients who are withdrawn from the study before the primary endpoint visit (week 24) will be asked to return to the clinic for study assessments described in [Table 1](#). Patients who are withdrawn from the study after the primary endpoint visit will be asked to return to the clinic for early termination assessments only.

9.1.3. Unscheduled Visits

All attempts should be made to keep patients on the study schedule. Unscheduled visits may be necessary to repeat testing following abnormal laboratory results, for follow-up of AEs, or for any other reason, as warranted.

9.2. Study Procedures

9.2.1. Procedures Performed Only at the Screening/Baseline Visit

The following procedures will be performed for the sole purpose of determining study eligibility or characterizing the baseline population: peanut SPT, HIV Ab, HBsAg, HBcAb, Hep C Ab, height. Demographics and medical history will be collected.

9.2.2. Efficacy Procedures

9.2.2.1. Double-Blind Placebo-Controlled Food Challenge

The patient's sensitivity to peanut allergen is defined as the dose at which the patient experiences allergic reactions. All symptoms and signs will be evaluated and rated based on a standardized oral food challenge scoring system (see [Appendix 2](#)). Up-dosing during the DBPCFC will be stopped when the blinded assessor finds symptoms and/or signs that indicate a definite objective allergic reaction (CoFAR grading system (see [Appendix 2](#)) has occurred based on clinically significant changes in reported symptoms, physical findings, or vital signs that the patient is experiencing to the challenge material. The challenge will consist of 8 doses (peanut or placebo), given every 15 to 30 minutes: 1, 3, 10, 30, 100, 300, 600, 1000 mg, up to 2044 mg peanut protein (cumulative). Both peanut and oat protein will be concealed in a food that masks the taste. The food challenges will be performed on different days (1 day placebo [oat] protein, 1 day peanut protein, with order determined at random) at least 24 hours, but not more than 7 days, apart and not within 24 hours of a dose of study drug. After the last dose of the DBPCFC, the patient will be monitored for at least 2 hours and then discharged from the clinic. Patients will be considered to have passed the DBPCFC if they do not experience any objective Grade 1 reaction by the CoFAR grading system (see [Appendix 2](#)). If the patient experiences reactions, they will be treated with the necessary rescue medications. Symptom severity will be adjudicated by an independent, blinded assessor who is not involved in performing the baseline food challenge.

